10.1 Cycle 1 - dose escalation phase only

If toxicity occurs between day 1 of cycle 1 and first dose of treatment administered in cycle 2 treatment of the dose escalation phase, please refer to Section 8.1.4 for DLT definitions.

Any patient experiencing a DLT during cycle 1 of the dose escalation phase will have his or her treatment withheld until toxicity resolves to baseline or Grade ≤ 1 . Upon resolution, the patient may have therapy re-instituted at the next lowest dose level, unless this occurs dose level -1, where patients will stop therapy.

If a patient experiences an SAE or grade 3/4 toxicity after the day 1 dose of cycle 1 (loading carfilzomib dose) treatment should be delayed until toxicity has resolved to baseline or Grade ≤ 1 and then discussed with the CI to see whether it is safe to proceed as planned.

If there is a greater than 8 day delay in dosing due to toxicity attributable to the loading dose of Carfilzomib, the safety review committee will be notified.

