10.5 Dose Reductions for Non-Haematologic Toxicities

Carfilzomib should be withheld for events \geq Grade 3 until resolved to \leq Grade 1 or return to baseline.

After resolution of the event to \leq Grade 1 or return to baseline, if the adverse event was not treatment-related, subsequent treatment with Carfilzomib may resume at full dose. If the event was treatment-related, subsequent treatment with Carfilzomib will resume at one level dose reduction except for nausea, vomiting or diarrhoea which can be attributed to Carfilzomib (see table 5 below). If toxicity continues or recurs, a 2nd Carfilzomib dose reduction may be permitted at the discretion of the investigator. No more than three dose reductions will be permitted in an individual participant on study. If toxicity continues or recurs after three dose reductions, the participant should be discontinued from treatment.

Dose reduction guide for Carfilzomib:

Table 4: Dose Reduction Guide for Carfilzomib Dosing

Current dose	Reduce to
27mg/m ²	20mg/m ²
36 mg/m ²	27 mg/m ²
45 mg/m ²	36 mg/m ²
56 mg/m ²	45 mg/m ²

If the participant tolerates the reduced dose for two cycles, participant may be dose escalated to the dose prior to reduction following discussion with the CI and CTRU.

Dose adjustment guidelines for non-haematologic toxicities are summarised as follows:

Table 5: Dose Adjustment Guidelines for Non-Haematological Toxicities.

Symptom	Recommended Action Carfilzomib
Allergic reaction/hypersensitivity Grade 2 – 3 Grade 4	Withhold until \leq Grade 1, reinstitute at full dose. Discontinue (refer to section 14)
Tumour lysis syndrome (≥ 3 of following: $\geq 50\%$ increase in creatinine, uric acid, or phosphate; $\geq 30\%$ increase in potassium; $\geq 20\%$ decrease in calcium; or ≥ 2 -fold increase in LDH)	Withhold Carfilzomib until all abnormalities in serum chemistries have resolved. Reinstitute at full doses.

Infection Grade 3 or 4	Withhold Carfilzomib until systemic treatment for infection complete and infection resolves. If no neutropenia, restart at same dose. If neutropenic, follow neutropenia instructions.
Herpes zoster of any grade	Withhold Carfilzomib until lesions are dry. Reinstigate at full dose
Grade 3 Nausea or vomiting despite maximal anti-emetic therapy or diarrhoea	Withhold Carfilzomib until this resolves and re-start at full dose. If recurrent, re-start at one dose level lower

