Grade 2 treatment emergent neuropathy with pain or Grade 3 neuropathy	Continue to dose. If neuropathy persists for more than two weeks hold Carfilzomib until resolved to \leq Gr 2 without pain. Then restart at 1 dose decrement
\geq Grade 3 elevation in LFTs (AST, ALT, or total bilirubin)	Withhold dose. Resume at 1 dose decrement when toxicity has resolved to baseline.
Grade 4 neuropathy	Discontinue (refer to section 14)
Renal Dysfunction Serum creatinine equal to or greater than 2 x baseline, or CrCl $<$ 15mL/min (or CrCl decreases to \leq 50% of baseline) or need for dialysis.	Withhold dose and continue monitoring renal function (serum creatinine or serum creatinine clearance). If attributable to Carfilzomib, resume when renal function has recovered to within 25% of baseline. Start at 1 dose level reduction. If not attributable to Carfilzomib, dosing may be resumed at the discretion of the physician. If tolerated, the reduced dose may be escalated to the previous dose at the discretion of the physician. For patients on dialysis during Carfilzomib, the dose is to be administered after the dialysis procedure.
Congestive heart failure and other cardiopulmonary disorders.	See section 10.10. Any participant with marked worsening of symptoms of congestive heart failure, whether or not drug related, must have the dose withheld until resolution or return to baseline, after which treatment may continue at a reduced dose, or the subject may be permanently discontinued
Other non-haematologic toxicity assessed as Carfilzomib-related \geq Grade 3	Withhold dose until toxicity resolves to \leq Grade 2 or baseline. Restart at 1 dose decrement. If tolerated, the reduced dose may be escalated to the previous dose at the discretion of the physician.
PRES (posterior reversible encephalopathy syndrome with symptoms including headaches, altered mental status, seizures, visual loss, and hypertension).	If PRES suspected, withhold Carfilzomib. Consider evaluation with neuroradiological imaging for onset of visual or neurological symptoms suggestive of PRES. If PRES diagnosis is excluded, Carfilzomib administration may resume if clinically appropriate.

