10.10 Congestive Heart Failure

New or worsening cardiac failure, myocardial ischaemia, and myocardial infarction have occurred following Carfilzomib administration, with the risk of cardiac failure increased in elderly subjects (≥ 75 years). Worsening of congestive cardiac failure and other cardiopulmonary disorders including pulmonary oedema, and decreased ejection fraction will need careful assessment in relation to baseline cardiac status for the patient since many amyloid patients will have stable heart failure prior to trial entry.

If left ventricular ejection fraction (LVEF) decreases occur (for resting LVEF < 40% or reduction of LVEF to <55% if the drop is greater than 20% from baseline), withhold Carfilzomib until LVEF returns to > 40% or, if held due to a drop, < 55% within 15% of baseline. Resume at a 1-dose decrement.

Any participant with marked worsening of symptoms of congestive heart failure, whether or not drug related, must have the dose withheld until resolution or return to baseline, after which treatment may continue at a reduced dose, or the subject may be permanently discontinued. If no resolution after 2 weeks, participant will be permanently discontinued.

Any participant with significant worsening symptoms of CHF which has not resolved with an increase in diuretics prior to the next dose, or any other acute cardiac event, whether or not drug related, must have treatment withheld until resolution. After the event has resolved, treatment may continue at the previous dose, or one dose level lower than the previous dose. If there is no resolution of worsening of CHF after 2 weeks or further worsening after the next dose, the participant will be discontinued from treatment.

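### Protocol section 10.10 gives two overlapping restart-dose rules for worsening heart failure symptoms, and a restart at the previous dose complies with one but not the other

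*Protocol*

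**What the plan says.** Protocol section 10.10 (Congestive Heart Failure) deals with worsening symptoms in two consecutive paragraphs.

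- **First trigger.** "Any participant with marked worsening of symptoms of congestive heart failure, whether or not drug related, must have the dose withheld until resolution". Recovery to the patient's starting state is accepted as well. The paragraph then lists what may follow: "after which treatment may continue at a reduced dose, or the subject may be permanently discontinued".
- **Second trigger.** "Any participant with significant worsening symptoms of CHF which has not resolved with an increase in diuretics prior to the next dose". The same paragraph also covers acute cardiac events of other kinds, again regardless of drug relationship. Treatment is withheld, and the rule on recovery is that "treatment may continue at the previous dose, or one dose level lower than the previous dose".

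The congestive heart failure row of Table 5 (section 10.5) refers the reader to section 10.10, but then repeats only the first rule: "treatment may continue at a reduced dose, or the subject may be permanently discontinued".

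Three other places give a restart dose that could apply to the same patient:

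- Section 10.5, general text: after a treatment-related event of Grade 3 or higher, carfilzomib resumes one level down, except for nausea, vomiting or diarrhoea.
- Section 10.1: after a DLT in cycle 1 of the escalation phase, "the patient may have therapy re-instituted at the next lowest dose level". Section 8.1.4 includes a heart failure criterion among the DLTs.
- Section 10.10, LVEF rule: "Resume at a 1-dose decrement". This has its own measured trigger and is not part of the conflict.

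**The concern.** *Marked* and *significant* are not tied to a CTCAE grade, an NYHA class or any measurement, and no sentence says which paragraph governs when both fit. Nor does the wording give a clear order of severity: the paragraph that allows the previous dose is the one for worsening that has not responded to more diuretic.

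If a site cannot tell which paragraph applies, patients with the same event could restart at different doses across the 15 planned centres, and each site could cite the protocol in support. That is first a patient-safety matter. It also reaches the data:

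- **Toxicity by cycle.** Grade 3 or 4 toxicity over all cycles is a primary endpoint (section 18.1), tabulated by cycle (section 19.3).
- **Relative dose intensity and dose reductions.** Both depend on the restart dose (sections 18.3 and 19.4).
- **Compliance.** Section 18.3 requires treatment as per protocol. Where the protocol gives two answers, that status cannot be settled.

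**Working it through.** The plan states no figure on this point, so the check sets the rules side by side and then sizes one dose step.

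**Step 1: compare the two paragraphs of section 10.10.**

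| Feature | First paragraph | Second paragraph |
|---|---|---|
| Trigger | Marked worsening of CHF symptoms | Significant worsening not resolved by more diuretic before the next dose; or another acute cardiac event |
| Drug relationship needed | No | No |
| Withhold treatment | Yes | Yes |
| Recovery standard | Resolution or return to baseline | Resolution |
| Restart options | Reduced dose, or stop for good | Previous dose, or one level lower |
| No resolution after 2 weeks | Discontinue | Discontinue |

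**Step 2: find the overlap.** Take a patient whose symptoms worsen markedly and have not resolved with more diuretic when the next dose is due. On any ordinary reading, marked worsening is also significant, so this patient meets both triggers. An acute cardiac event without worsening CHF symptoms meets only the second.

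**Step 3: test each restart choice for that patient, after recovery.**

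- Previous dose: listed by the second paragraph; not listed by the first or by Table 5.
- One level lower: listed by the second paragraph, and a reduced dose under the first. Complies with both.
- Permanent discontinuation: listed by the first paragraph; not among the second paragraph's options after resolution, though both are worded as permission to continue.

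The practical conflict is therefore over the previous dose.

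**Step 4: compare with sections 10.5 and 10.1.** For a treatment-related event of Grade 3 or higher, the general text of 10.5 calls for one level down, while the second paragraph of 10.10 offers the previous dose even when the event is drug related. For a cycle 1 DLT in escalation, 10.1 gives the next lowest level. The overlap there is close: the DLT criterion in 8.1.4 includes heart failure symptoms persisting at Grade 3 or higher despite more oral diuretic, which resembles the second trigger in 10.10.

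**Step 5: size of one level.** Inputs are from "Table 4: Dose Reduction Guide for Carfilzomib Dosing". Gap = (previous dose − reduced dose) / previous dose.

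| Previous (mg/m²) | One level lower (mg/m²) | Gap |
|---|---|---|
| 56 | 45 | 11/56 = 19.6% |
| 45 | 36 | 9/45 = 20.0% |
| 36 | 27 | 9/36 = 25.0% |
| 27 | 20 | 7/27 = 25.9% |

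An affected patient could restart at 100% of the previous dose under one paragraph, or at about 74% to 80% of it after a one-level reduction under the other.

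**The case against.** The best defence is that the paragraphs form two tiers: marked worsening leads to reduction or stopping, and significant worsening to the previous dose or one level lower. Both are permissive, both withhold treatment, both discontinue after two weeks without resolution, and one level lower satisfies each. Table 5 defers to 10.10 and so is not an independent third rule. Sections 10.1 and 10.5 already point towards reduction for cycle 1 DLTs and for severe related events, which leaves the previous-dose option mainly for unrelated or lower-grade events.

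Much of this stands, and it narrows the point. It does not remove it. A two-tier reading needs a boundary between the tiers, and the protocol gives none. Nothing says that 10.1 or 10.5 overrides 10.10, and Table 5 itself contains event-specific rows that depart from the general text of 10.5, so a site could reasonably treat 10.10 as another such exception.

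Stronger readings that a reader might infer, and that the documents do not support:

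- *Every patient with worsening heart failure is affected.* Only those who meet both triggers, or cannot be placed clearly under one, recover in time, and are restarted at the previous dose.
- *The second paragraph allows a full-dose restart.* It says previous dose, which may already be a reduced one.
- *Section 2.1.3.4 shows how common the problem would be, with cardiac events of Grade 3 or higher in 4 of 11 patients.* Those 4 include a cardiac arrest from ventricular tachycardia and an exacerbation of atrial fibrillation; only two are linked to manifestations of CHF. The figure of 11 evaluable patients is attached to drug-related events, not to this count. That study also dosed twice weekly.

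**Conclusion.** The inconsistency is real but narrow. Section 10.10 gives two restart rules whose triggers overlap, with undefined terms and no precedence. In the overlap, a restart at the previous dose complies with one paragraph and not with the other or the Table 5 row, and it sits uneasily with sections 10.1 and 10.5.

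The difference is one carfilzomib level, 19.6% to 25.9% of the previous dose, assuming that the alternative is a one-level reduction as in Table 4. The documents give no basis for estimating how many patients would be affected.

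The consequences are for patient safety, toxicity in later cycles, relative dose intensity, the count of dose reductions, and compliance. The statistical effect is limited, because all these analyses are descriptive. A patient whose heart failure event was itself Grade 3 or 4 already counts in the all-cycles toxicity proportion, so for that patient the restart dose would show in the by-cycle tables.

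A reader might also infer that the MTD or RD is put in doubt. The documents do not show that: the MTD rests on DLTs in the cycle 1 window, and a heart failure DLT is counted before any restart dose is chosen.

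**What to change.** Amend the protocol so that each heart failure event has one restart rule:

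1. Define *marked* and *significant* by a stated grade, class or measurement, or merge the two paragraphs of 10.10.
2. Align the Table 5 row with the result.
3. State how 10.10 relates to the general rule in 10.5 and to the cycle 1 DLT rule in 10.1, including which governs when more than one applies.
4. In the same edit, settle whether recovery means resolution only, or also return to baseline. The paragraphs differ, and 10.10 itself notes that many patients enter with stable heart failure.

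The choice of restart rule is clinical and is for the clinical team. The cost is a wording amendment; the design, sample size and SAP analyses do not change.

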10.11 Conditions Not Requiring Dose Reduction

The following conditions are exceptions to the above guidelines. Carfilzomib dosing does not need to be withheld in the following cases:

- Grade 3 nausea, vomiting or diarrhoea (unless persisting >5 days with adequate use of anti-emetics or anti-diarrhoeal medication)
- Grade 3 fatigue (unless persisting for >14 days)

- Alopecia
- \geq Grade 3 hyperglycaemia attributed to Dexamethasone

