8.1.4 Dose Limiting Toxicities

Dose limiting toxicities (DLTs) will be collected from the time of receiving the first dose of Carfilzomib in cycle 1 up to the first dose of treatment administered in cycle 2. Only DLTs that are attributed to the registered dose of Carfilzomib will be included when determining the MTD (i.e those attributed to the loading dose will be excluded) (see section 19.2). A DLT will be defined as any of the following events that are determined to be related to trial drug administration:

1. Any non-haematological toxicity ≥ Grade 3 according to NCI CTCAE Version 4.03 which fails to return to ≤Grade 1 or baseline after 7 days. Nausea, vomiting, diarrhoea and electrolyte imbalances will be considered DLTs only if they reach ≥ Grade 3 severity despite adequate supportive care measures. Similarly, fluid retention or worsening symptoms of heart failure will be considered as DLTs if they are persistent ≥Grade 3 despite increase in oral diuretics or there is an increase in dyspnoea by ≥ 2 NYHA grades within 12 hours of administration of Carfilzomib which persists for > 6 hours or needs hospital admission
2. Grade 4 neutropenia lasting > 7 days or Grade 4 neutropenia with sepsis despite adequate supportive measures.
3. Any grade 4 thrombocytopenia which fails to return to Grade 2 within 7 days without platelet support
4. Delay of >8 days within cycle 1 or delay of commencement of 2nd cycle by more than 14 days, due to significant toxicity or tolerability issue*
5. Any other event which, in the opinion of the Safety Review Committee, is considered to be clinically significant and related to treatment

*This will not be defined as a DLT if the delay is due to one of the other specified DLT criteria.

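### Protocol 8.1.4, 10.1, 10.11 and Table 5 give conflicting carfilzomib instructions for the same toxicity, and none is said to prevail in cycle 1 of escalation

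*Protocol*

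**What the plan says.** - **DLT definition (Protocol 8.1.4, repeated in SAP 2.3.1).** A related non-haematological event of grade 3 or more is a DLT if it is one "which fails to return to ≤Grade 1 or baseline after 7 days". Fatigue and neuropathy have no separate rule. Nausea, vomiting, diarrhoea and electrolyte disturbance "will be considered DLTs only if they reach ≥ Grade 3 severity despite adequate supportive care measures".
- **Cycle 1 of escalation (10.1).** "Any patient experiencing a DLT during cycle 1 of the dose escalation phase will have his or her treatment withheld until toxicity resolves". The recovery target is grade 1 or less, or the patient's baseline. After that, "Upon resolution, the patient may have therapy re-instituted at the next lowest dose level"; at level -1 therapy stops instead. A separate paragraph delays treatment for any grade 3/4 toxicity after the loading dose, with no minimum duration.
- **Later cycles (10.2) and the opening of 10.5.** Both hold treatment for grade 3 or higher non-haematological events. The last sentence of 10.2 sends toxicities seen at any time to Tables 3 and 5, but leaves out neuropathic pain and peripheral sensory neuropathy.
- **Table 5, neuropathy (grade 3, or grade 2 with pain).** "Continue to dose. If neuropathy persists for more than two weeks hold Carfilzomib until resolved to" grade 2 or lower without pain, then restart one decrement lower.
- **Table 5, grade 3 nausea or vomiting despite maximal anti-emetics, or diarrhoea.** "Withhold Carfilzomib until this resolves and re-start at full dose"; the lower level applies only on recurrence.
- **Exceptions (10.11).** No carfilzomib hold is needed for "Grade 3 fatigue (unless persisting for >14 days", for grade 3 nausea, vomiting or diarrhoea unless it goes beyond 5 days on adequate medication, or for grade 3 or higher hyperglycaemia attributed to dexamethasone, which has no time limit.

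Neither document says which of these sections prevails in cycle 1 of escalation. The SAP does not deal with dosing.

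**The concern.** A patient in cycle 1 of escalation can meet the DLT definition and be subject to two printed dosing instructions at once. A site that follows 10.1 holds; a site that follows 10.11, or the neuropathy row of Table 5, may give the next dose at the full registered level. At stake is whether patients whose toxicity the protocol itself calls dose limiting are handled alike across the 15 planned centres.

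Fatigue is a plausible place for this to arise. In the single-agent AL amyloidosis study described in Protocol 2.1.3.4, which 2.3.1 uses to justify the doses, the DLTs that set the MTD were grade 3 fatigue of at least 7 days, in 2 of 4 patients at 45 mg/m².

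**Working it through.** The plan has no figure to reproduce. The check sets the duration limits side by side and asks which onset days produce opposite instructions on a scheduled dosing day.

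**Inputs.** Carfilzomib is given on days 1 (loading dose), 8 and 15 of a 28-day cycle (8.1.1), so cycle 2 day 1 is nominally day 28 + 1 = 29. For onset on day *o*, the event has lasted *d* − *o* days at dose day *d*.

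**Fatigue (10.11) and grade 3 neuropathy (Table 5).** The event is a DLT, so held under 10.1, when *d* − *o* > 7. No hold is called for by 10.11 or Table 5 while *d* − *o* ≤ 14. The instructions conflict when 7 < *d* − *o* ≤ 14, that is, for *o* from *d* − 14 to *d* − 8.

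| Dose day | Onset days in conflict | Duration at that dose |
|---|---|---|
| 8 | none | – |
| 15 | 1 to 7 | 14 down to 8 days |
| 29 (cycle 2 day 1) | 15 to 21 | 14 down to 8 days |

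If the DLT clause is read as 7 days or more, onset day 1 (day 8 dose), day 8 (day 15 dose) and day 22 (day 29 dose) are added.

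**Day 8 dose.** The loading-dose paragraph of 10.1 has no minimum duration. Grade 3 fatigue starting on days 1 to 8, before that dose, has lasted at most 7 days, so 10.1 delays and 10.11 requires no hold. The day 15 conflict for onset on days 1 to 7 therefore arises mainly where a site has already followed 10.11 on day 8.

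**Neuropathy in every cycle.** The opening of 10.5 and 10.2 hold for grade 3 events, while the Table 5 row continues dosing for two weeks. In addition, 10.2 takes neuropathic pain and peripheral sensory neuropathy out of the tables, although Table 5 has a row for neuropathy with pain. Grade 2 neuropathy with pain is not a DLT under the first criterion of 8.1.4, so the DLT conflict concerns grade 3 only.

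**Nausea, vomiting, diarrhoea.**
- If the 7-day clause does not cover these events, a grade 3 event despite supportive care is a DLT at once. It conflicts with 10.11 when 0 ≤ *d* − *o* ≤ 5: onset days 3–8, 10–15 and 24–29 for doses on days 8, 15 and 29.
- If the clause does cover them, a conflict needs *d* − *o* > 7 and ≤ 5 together, which is impossible. Section 10.11 does not then contradict 8.1.4.
- On either reading, Table 5 withholds where 10.11 requires no hold, and the loading-dose paragraph of 10.1 differs from 10.11. Table 5 restarts at full dose after a first event; 10.1 restarts one level lower if the event is a DLT.

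**Hyperglycaemia.** Dexamethasone is an investigational product (9.1), and 8.1.4 counts events related to trial drug administration, so a persistent event could be a DLT while 10.11 requires no hold. Only DLTs attributed to the registered carfilzomib dose determine the MTD, so the effect there is likely small.

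**The case against.** **Headings already settle precedence.** Section 10.1 is headed for cycle 1 of escalation and 10.2 for subsequent cycles, so the specific rule would naturally govern cycle 1. This is a fair reading, but it is not written down. Section 10.11 describes itself as an exception to the guidance above it, which includes 10.1, and has no cycle limit. The last sentence of 10.2 applies Table 5 to toxicities at any time. If the exception sentence is given effect, it reaches 10.1; if it is not, 10.11 contradicts Table 5 on gut toxicity. The neuropathy conflict in later cycles remains either way.

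**Section 10.11 only permits.** This stands: a site that holds breaches nothing in 10.11, and only the neuropathy row of Table 5 directs continued dosing. But a permission set against a mandatory hold still lets two sites treat the same patient differently.

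**Stronger readings that the documents do not support.**
- A reader might infer that Table 5 continues dosing through gut toxicity. It withholds.
- A reader might infer that 10.1 ends treatment after a DLT. It withholds and allows a lower restart; therapy ends outright only at level -1.
- A reader might infer that DLT counts, and so the MTD, become non-comparable between sites. The event counts under 8.1.4 whether or not the site holds, and the Safety Review Committee reviews each DLT. The cycle 2 day 1 dose closes the DLT window, so it adds no exposure inside it. Onset on days 1 to 7 follows only the loading dose, and DLTs attributed to that dose are excluded from the MTD. The footnote to the delay criterion excludes delays caused by another DLT criterion, which largely closes that route.

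**Fatigue may be less likely here.** The earlier fatigue DLTs arose at 45 mg/m² twice weekly, 2 × 45 = 90 mg/m² per week. This trial's top level is 56 mg/m² once weekly, with thalidomide added. Calling fatigue the likely DLT would be extrapolation; calling it plausible is not.

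**Conclusion.** The instructions conflict and should be corrected. For related grade 3 fatigue or neuropathy lasting 8 to 14 days, 10.1 withholds, while 10.11 needs no hold for fatigue and Table 5 directs dosing for neuropathy. The clearest case is cycle 2 day 1, for onset on days 15 to 21. Table 5 and 10.11 also disagree on holding for grade 3 gut toxicity; whether 10.11 further conflicts with 8.1.4 depends on an unclear clause. Hyperglycaemia is minor.

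The consequence is inconsistent dosing: by following a printed rule, a site can give another full registered dose to a patient who meets the DLT definition. A bias in DLT counts or in the MTD is not shown. The calendar assumes on-schedule dosing, events judged related to trial drug, and the 7-day clause read as more than 7 days. How often such events will occur cannot be derived from the documents.

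**What to change.** - Reconcile 8.1.4, 10.1, 10.2, 10.5, Table 5 and 10.11 so that fatigue, neuropathy, nausea/vomiting/diarrhoea and dexamethasone-attributed hyperglycaemia each have one instruction.
- State in 10.11 and Table 5 whether they apply in cycle 1 of escalation, and which section prevails there.
- State in 8.1.4 (and SAP 2.3.1) whether the 7-day clause covers nausea, vomiting and diarrhoea.
- Resolve whether neuropathy is managed under Table 5, given the exclusion in 10.2.

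Which instruction is right in each case is for the clinical team. The cost is a protocol wording amendment, a matching line in the SAP and a note to sites. No further patients or data are needed.
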